The primary objective of this study is to examine in a double blinded and randomized trial the efficacy of Recombinant Human lactoferrin (rhLF) in reducing chronic inflammation as measured by IL-6 and sTNFR1 in the bloodstream. Secondary objectives include assessing the efficacy of rhlactoferrin (rhLF) in attenuating cognitive decline as measured by the Digit Symbol Substitution Test and Trail Making Test, as well as improving physical mobility as measured by performance on 4 meter and six-minute walk tests. The tertiary objective of this study is to gather information about the tolerability of and adherence to oral rhlactoferrin (rhLF) among older adults with CI over a three-month period.

3. Background

Chronic Inflammation and Biological Mediators:

Chronic inflammation (CI) as defined by chronic elevation in serum inflammatory measures is a known risk factor for a host of adverse health outcomes in older adults (3;17;18). The etiology of CI is complex with increased chronic disease burden, fat mass, free radicals, and senescent cells, dysfunctional mitochondria, altered microbiome, and decreased GI tract barrier function all potentially contributing (19-25). Dozens of population studies have detailed significant associations between pro-inflammatory measures and functional and mobility decline, frailty, worsening chronic illness, cognitive decline, mortality and reduced gait speed (1;2;26;27;28). Although these relationships were often considered to be epidemiological phenomena rather than causal, evidence suggests that chronic exposure to some inflammatory mediators can lead directly to molecular and tissue changes that contribute to the observed adverse outcomes (29;30-34). Specifically, evidence suggests that IL-6, sTNFR1 and other molecules directly and negatively impact skeletal muscle and neurologic tissue through impairment of satellite cells, through the triggering of cell death pathways, and through other mechanisms (35-44). Figure 1 provides a conceptual overview for a biologically plausible pathway between CI and health-related declines; lactoferrin is hypothesized to impact inflammatory mediators and their downstream effects.

Chronic Inflammation and Cognitive Decline:

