Baseline Visit (BV): Individuals meeting eligibility criteria (described below) will be scheduled for a baseline visit. This visit will consist of a brief medical history review and blood draw, along with outcome measurements described thoroughly below. At the end of the visit, the pharmacy or site coordinator will distribute the randomized study product with instructions. A structured walking program and encouragement of physical activity for participants in all treatment arms will be included. Participants will also receive an accelerometer for home mobility measurement along with detailed instructions for use.

Follow up visit (FUV): Monthly in person visits will take place, with telephone contact every two weeks by study staff between visits to help maintain adherence and assess for adverse effects. Pill counts and side effect assessments will take place at FU1, FU2, and FU3. FU6 will include measures checked in Table 2 and described below.

Table 2

	PSC	SV	ABT	BV	FU1	FU2	FU3			FU6.
Phone Screen	X									
Medical History		X								
Brief Medical History Review				X	X	X	X			X
Informed Consent		X								
Demographics		X								
Randomization				X						
Frailty Assessment				X			X			X
Activity Assessment				X			X			X
Vital Signs (BP, HR, Hgt,Wgt. Temp, Resp.)		X	X	X	X	X	X			X
Short Physical Performance Battery				X			X			X
Side Effect Assessment					X	X	X			
4 meter walk		X		X			X			X
Six-minute walk test				X			X			X
Blood Draw		X	X	X	X		X			X
Physical Exam		X								
MMSE		X								
Cognitive measures (Trail Making Test and Digit Symbol Substitution Test)				X			X			X
Accelerometry				X			X			X
Pill Calendar				Marked Daily to end of Month 3						
Abbreviations: PSC: Prescreening contact; SV: Screening visit; ABT Additional Blood test (to further determine eligibility for those whose cytokine levels are above threshold); BV: Baseline visit; FU1-6: Follow up months 1-6 of pilot study										

All laboratory results will be reviewed by study physicians during the study and there will be frequent review

of adverse and/or other unexpected events. Following study protocol, all adverse events will be reported to the IRB and National Institute on Aging (NIA) as per requirements. Participants will be able to report issues at study contacts but will also be provided with a number to call ad hoc as needed if issues related to study participation arise. If participants choose to withdraw from the study, their medical care will not be affected in any way.

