Measurements Performed at Visits:

Phlebotomy (primary outcome measure): Primary outcome will be serum IL-6 and sTNFR1 as measured by ELISA as previously performed in the PI's laboratory by an experienced laboratory technician. Blood will also be measured for CBC w/Diff, and CMP, these measures will be made from blood drawn at SV, ABT, BV, FU1, FU3 and FU6. Rationale for the choice of these measures are provided above in the background section.

A Physical Exam will be taken at SV. A Medical History will be taken at SV and a Brief Medical History Review at BV and all subsequent FUV. These are to assess eligibility or contraindicate the intervention, detect new conditions or complications and other safety signals, and to measure important covariates (i.e. demographics, past medical history, current activity levels, routine medication, and vitamin use).

4 meter walk: Speed of walking at usual pace over 4 meters will be measured at the SV, BV, FU3, and FU6.

Six-minute walk: This is performed at the BV, FU3, and FU6 by having the participant walk along a straight hallway for six minutes and measuring the distance walked and the sensation of leg fatigue and dyspnea. The participant is given scripted prompts at one-minute intervals, but the test is largely self-directed and self-limited.

Short Physical Performance Battery (SPPB): This is an assessment of lower extremity functioning comprised of gait speed, balance, and leg strength and is performed at the BV and FU6. As part of the SPPB, participants will complete a balance test assessing their ability to stand without assistance and a chair stand test.

Cognitive Function Measures: The Digit Symbol Substitution Test (DSST) is a sensitive measure in cognitively normal older adults. It measures attentional control and switching, and more broadly executive processes and thus is not sensitive to impairment in particular brain regions. It is a highly precise measure across the range from cognitively normal to mildly impaired older adults and takes about 90 seconds to administer (75). The DSST will be conducted at BV, FU3, and FU6. The Trail Making A and B Test measures executive functioning and task-switching, is highly sensitive to change and takes 5-10 minutes to administer (76). This test will be performed at BV, FU3, and FU6. An MMSE (a mini-mental state exam) will also be performed at the BV.

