Side Effect Assessment: A Side Effect Assessment will be conducted at FU1, FU2, and FU3. The purpose of this assessment is to monitor participants' responses to lactoferrin and to assess for any adverse side effects.

Activity Assessment: Participants will answer questions about their physical activity and energy levels. This assessment is conducted at BV, FU3, and FU6.

Frailty Assessment: This assessment is completed at BV, FU3, and FU6. This assessment measures participants' walking speed and grip strength, and includes questions about weight loss.

Vital Signs: Participants' vital signs will be measured at every study visit. These measurements include height, weight, blood pressure, respiratory rate, and temperature.

Additional Physical and Functional Measurements:

Home Mobility Measurement: An Acti-Graph® Link Activity monitor will be placed on the participant's non-dominant wrist at the end of the BV. This model includes an ambient light designed to provide environmental information and a gyroscope and magnetometer to capture position and rotational data. Accelerometry counts will be measured at a sampling frequency of 80 hertz for 7 days immediately

after completing the BV, 3-month, and 6-month visits. Participants will be asked to wear the device at all times except when swimming for >30 minutes. Monitors will be mailed via pre-addressed express mail packets where all raw data will be downloaded using commercial software (ACTLIFE, v6) to derive activity data in g force and counts/min. The JHU Statistical Methods for Applications and Research in Technology ("SMART"-stats) group, developers of the "movelets" technology that enables the use of raw data (62), will use collected data to: (i) characterize cumulative daily activity, (ii) assess daily circadian patterns of activity, (iii) assess physical activity variability, (iv) model patterns of daily activity, and (iv) estimate walking speed (62, 63, 64). These measurements greatly extend what is normally available from accelerometers and will complement mobility measures by describing function enacted in daily life.

5. Inclusion/Exclusion Criteria

Inclusion: Age 70 and older; able to complete 4- meter timed walk; walking speed ≤ 1.0 m/sec; serum IL-6 level ≥ 2.5 pg/ml or TNFR1 level ≥ 1500 pg/ml. Consistent with NIH guidelines, both genders and minority persons are enrolled. Participants will be followed for 6 months to investigate the effects of the treatments on gait speed and other outcomes.

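### The Side Effect Assessment has no pre-dose administration, so symptoms already present cannot be separated like for like from new or worsened ones

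*Combined protocol and SAP*

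**What the plan says.** Section 2 (Objectives) sets a tertiary aim to "gather information about the tolerability of and adherence to oral rhlactoferrin (rhLF) among older adults with CI over a three-month period".

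The timing of the form is stated three times, consistently. Section 4, under the follow-up visits, says "Pill counts and side effect assessments will take place at FU1, FU2, and FU3". Under Measurements Performed at Visits it says "A Side Effect Assessment will be conducted at FU1, FU2, and FU3". Table 2 marks the same three visits and leaves the BV column empty for this row. The stated purpose is this: "The purpose of this assessment is to monitor participants' responses to lactoferrin and to assess for any adverse side effects".

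On the start of product, the Baseline Visit paragraph says "At the end of the visit, the pharmacy or site coordinator will distribute the randomized study product with instructions".

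Other health information is collected around the same time:
- On histories: "A Medical History will be taken at SV and a Brief Medical History Review at BV and all subsequent FUV". These are meant in part to pick up new conditions.
- The screening visit (SV) also has a physical exam and a questionnaire that takes in fatigue.
- The Activity Assessment at BV, FU3 and FU6 asks about energy levels.
- Between visits there are calls: "with telephone contact every two weeks by study staff between visits to help maintain adherence and assess for adverse effects".

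The documents do not show the content of the form, do not define a side effect as new or worsened since baseline, and specify no tolerability analysis.

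**The concern.** A response to product is a change, and reading a change needs a starting value on the same scale. Table 2 follows that logic for the walks, the physical performance battery, frailty, activity, cognition and accelerometry, all of which have a BV reading. The Side Effect Assessment does not.

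Participants are aged 70 or over, with slow gait and raised inflammatory markers, so long-standing complaints, bowel symptoms for example, are to be expected. If someone reports such a complaint at FU1, nothing on the same form shows whether it was there before the first capsule. Two things are at stake: the absolute rate of side effects in each arm, and the precision of any side-by-side description of the arms. The Abstract says the pilot will be used to develop a more definitive trial, so both figures are likely to be carried forward. A pre-dose answer cannot be recovered once dosing has begun.

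**Working it through.** The plan states no figure for tolerability, so there is none to reproduce. Its sample size for logIL-6 does reproduce (a two-sample t-test at 0.86 SD needs 22.2, so 23 per group; power at 23 is 81.4%), but it does not bear on this point.

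**Inputs.** From the Abstract: n = 30 per arm. Assumed, because the documents give no symptom rates: pre-dose prevalence p of a given symptom of 20%, 30% or 40%.

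**Step 1: chance imbalance before any dose.** The SD of the between-arm difference in prevalence is √(2p(1−p)/30). The chance of a difference of at least three people (10 points) is the exact sum of b(x; 30, p)·b(y; 30, p) over all x, y with |x − y| ≥ 3.

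| p | SD of difference | P(differ by ≥ 3 people) |
|---|---|---|
| 20% | √(0.32/30) = 0.103 | 0.417 |
| 30% | √(0.42/30) = 0.118 | 0.481 |
| 40% | √(0.48/30) = 0.126 | 0.510 |

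At 10% prevalence the figures are 0.077 and 0.275. A gap of 20 points or more is much rarer: 0.075, 0.120 and 0.147 at 20%, 30% and 40%.

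**Step 2: possible inflation of absolute rates.** Suppose, as an upper-end illustration, that the form records every current symptom, that pre-dose symptoms persist, and that 10% of symptom-free participants in either arm develop the symptom. The reported rate is p + 0.1(1−p), the new-onset rate is 0.1(1−p), and the pre-existing share is p divided by the reported rate.

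| p | Reported | New onset | Pre-existing share | SD of arm difference: all reports / new onset only |
|---|---|---|---|---|
| 20% | 28% | 8% | 0.20/0.28 = 71% | 0.116 / 0.070 |
| 30% | 37% | 7% | 0.30/0.37 = 81% | 0.125 / 0.066 |
| 40% | 46% | 6% | 0.40/0.46 = 87% | 0.129 / 0.061 |

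With 80% persistence instead of full persistence, the shares are 66%, 76% and 82%.

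**Step 3: gain from adjusting for a BV answer.** If the pre-dose and on-treatment answers correlate at r (assumed), linear adjustment leaves a fraction 1 − r² of the variance of the arm comparison.

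| r | Variance left | Reduction |
|---|---|---|
| 0.3 | 0.91 | 9% |
| 0.5 | 0.75 | 25% |
| 0.7 | 0.51 | 49% |

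This gain belongs to adjustment. It does not carry over to a count of new or worsened symptoms, for which Step 2 is the relevant illustration.

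**The case against.** The strongest reply is that the trial already has what it needs for a tertiary, information-gathering aim. Placebo control, randomisation and blinding mean that pre-existing symptoms raise both arms equally on average. Chance imbalance is ordinary sampling error, which an interval estimate already covers. No between-arm test of tolerability is planned. Histories at SV and BV, the exam, and the fatigue and energy questions give the staff a pre-dose picture, and the calls ask about adverse effects before FU1.

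Much of this stands, and it rules out four stronger readings that a reader might infer:
- **That pre-existing symptoms will be counted as side effects.** No counting rule is given and the form is not shown. A form asking only about problems since starting product would fit its stated purpose. The defensible statement is that nothing in the plan separates old from new.
- **That the arm comparison is biased.** The design excludes systematic bias. The cost is inflated rates and lost precision.
- **That there is no pre-dose symptom information.** Fatigue and energy are asked about before dosing, and the histories give partial cover.
- **That physicians must judge the relatedness of each complaint without a baseline.** The judgement described in the Data and Safety Monitoring Plan concerns expedited reporting of serious, unexpected events, and the SV and BV records would be available for it.

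The reply does not close the gap. Nothing says that the histories record symptoms item by item on the same form, and the calls come after dosing has begun. An interval does cover the imbalance, but it is wider than it needs to be when a pre-dose answer could be had so cheaply.

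**Conclusion.** The point holds as a cheap, low-priority improvement. The schedule gives no like-for-like pre-dose answer on the dedicated tolerability form, and the other baseline information fills the gap only in part. Absolute side-effect rates may be inflated in both arms. With 30 per arm and an assumed pre-dose prevalence of 20% to 40%, the descriptive comparison carries chance imbalance with an SD of 10 to 13 points, and a 42% to 51% chance that the arms differ by three or more people before dosing. The prevalences, persistence, new-onset rate and correlations are all assumptions. The inflation figures also depend on the form recording all current symptoms, which the documents neither confirm nor exclude.

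**What to change.** Add a BV mark to the Side Effect Assessment row of Table 2, and BV to the matching statements of timing in Section 4. Use the same form, completed before product is handed out. Add one sentence on reporting: tolerability will be described by arm as symptoms new or worse than at BV, or as on-treatment reports adjusted for the BV answer. If the form now asks only about problems since starting product, it needs wording that works before dosing.

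The cost is a few minutes at a visit that already takes place and small edits to the text. There is no extra visit or procedure, and the sample size does not change.

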Most prior studies linking CI to adverse health in older adults have relied on single serum-based biomarkers such as IL6 or C-reactive protein (CRP). Studies have emerged that demonstrate that elevations in ≥2 inflammatory markers are more strongly associated with adverse outcomes (53-57). Approaches to aggregate markers can be categorized into “unsupervised” and “supervised”, with unsupervised aggregation being a summary of markers obtained based only on their joint distribution, e.g. by z-scores, principal component analysis or exploratory factor analysis (58;60) and supervised aggregation also considering biological understanding, or externally validating response (e.g., mortality(26)) for an “optimally” predicting response. Our group has made key contributions to work on supervised aggregation of inflammatory markers; including the first study applying latent variable (LV) modeling to summarize markers in accordance with biology understanding (61). Subsequently, we demonstrated that an inflammatory index (IIS) combining serum levels of IL6 and sTNFR1 provided superior prediction of 10-year mortality in the Cardiovascular Health Study (N=5,177) (26) over many other cytokines. As rationale for the use of these measures for diagnosis of CI in this project over other markers, we performed additional analyses (table 1) using the likelihood ratio test that shows that IL-6, TNFR1, and combined measure IIS are superior predictors of gait speed declines over 10 years when compared to CRP and interleukin 1 receptor antagonist (IL1RA). The cutoff

point for the study inclusion criteria for IL6 was identified based on a published threshold serum value above which adverse outcomes are much more common; the value for sTNFR1 was identified using a loess curve generated from data analyzed from the Cardiovascular Health Study (17;18;26). This background research provides strong rationale for the use of these measures to identify CI and to monitor treatment efficacy of lactoferrin on CI.

4. Study Procedures

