Prescreening Contact: Subjects will be recruited from a registry of older adults who have consented to be re-contacted for studies related to aging as well as from other populations of community-dwelling older adults. Sixty individuals age 70 and over who can walk without assistance at least four meters will be studied. Study coordinators will review basic information available from the registry and make a determination on potential eligibility based on the inclusion and exclusion criteria; this information includes participants’ age, ambulatory ability, and medical and neurological conditions that may exclude participation. Subjects who satisfy entry criteria will be contacted by the study coordinator or the

investigators, who will explain the study, its purpose, and its potential benefits and risks. Individuals will then be scheduled to visit Johns Hopkins Bayview for informed consent and the formal screening visit.

Screening Visit (SV): The screening visit will consist of the administration and review of the informed consent, completion of a demographic questionnaire, a medical history questionnaire, physical activity, fatigue and weight loss questionnaire, a MMSE, a physical exam, and measurements of vital signs (Height, weight, blood pressure, temperature and respiration) and two timed 4 meter walks. Blood will be drawn to measure CMP and CBC/w Diff; additionally a 10 cc tube of blood will be drawn, serum will be processed and stored at -80 C in the Primary Investigator’s laboratory for cytokine measurement. If the cytokine levels are above the threshold for either IL-6 or TNF-R1, we will retest the prospective participant again within four weeks to confirm chronic inflammation after screening visit. This will be done at the ABT visit. (17; 18; 26). If they remain eligible by elevation of either cytokine, they will be included in the study. If eligible, the participant will be randomized to either active or placebo treatment group. After confirming eligibility the JHU Pharmacy will generate the randomization schedule, and the appropriate numbered treatment kit for that participant will be assigned.

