Based on a two-sided two-sample t-test with a Type I error of 0.05, a sample size of 23 subjects per group (46 in total) will achieve 80% power to detect a difference of 0.86 SD or greater in logIL-6 between the treatment group and the placebo group at the end of the 6-month trial. Secondly, we will compare the linear rate of change in logIL-6 between the treatment and the placebo groups by modeling the individual trajectories of the outcome. With 20 subjects per group, three repeated measurements of IL-6 assessed at baseline, 3, and 6 months, and a correlation of 0.54 between measurements, we will have 80% power to detect a difference of 1.3 SD units (equivalent to a cross-sectional between-group difference of 0.65SD different at 6 months) or greater in the yearly rate of change in logIL-6 between the treatment and the placebo group. The within subject between-measurement correlation of 0.54 was estimated using longitudinal data from the Women's Health and Aging Study II. Therefore, using longitudinal data, we will have adequate power to detect a difference similar to the 0.63 SD (or 2.5 pg/mL) difference observed at the end of a 6-month, randomized clinical study of a ribonuclease-enriched lactoferrin supplement in post-menopausal women (16). Given these calculations, we are aiming to recruit up to 60 individuals, 30 in each group, in order to maximize our ability to detect differences between treatment and placebo groups. This increased number beyond what are calculated here will take into account anticipated drop outs during the treatment period and leave us with an estimated 'complete completer' group of 46 total. In addition, we are estimating that we will need to have at least 250 individuals recruited into the protocol in order to identify those eligible by inflammatory mediator criteria listed above.

8. Risks

Six Minute Walk Test: This is performed by having the participant walk along a straight hallway for six minutes and measuring the distance walked and the sensation of leg fatigue and dyspnea. The participant may stop at any time if they feel uncomfortable. As with any exercise test, there is a theoretical risk that a participant could suffer cardiac risk from arrhythmia or ischemia, or orthopedic risk from falling or stumbling. Risks are minimized by conducting the test in a medically supervised environment with trained personnel.

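### Either raised marker allows entry, yet the 6-month logIL-6 comparison is an unadjusted t-test with no stratification by entry marker or adjustment for starting IL-6

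*Combined protocol and SAP*

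**What the plan says.** Section 5 (Inclusion/Exclusion Criteria) sets the marker criterion as "serum IL-6 level ≥ 2.5 pg/ml or TNFR1 level ≥ 1500 pg/ml". Section 4 (Screening Visit) has people above either threshold retested within four weeks, again on an either-marker basis: "If they remain eligible by elevation of either cytokine, they will be included in the study". Someone with raised TNFR1 and IL-6 below 2.5 pg/ml at both tests can therefore be randomised. Section 4 says that the pharmacy generates the randomisation schedule and describes no stratification factor.

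Section 4 (Measurements Performed at Visits) names both markers as primary: "Primary outcome will be serum IL-6 and sTNFR1 as measured by ELISA". Section 7 gives analyses and power for logIL-6 only. The first is a two-sided t-test at the 0.05 level at 6 months, sized at 23 per group for 80% power. Its target effect is "a difference of 0.86 SD or greater in logIL-6 between the treatment group and the placebo group". The second compares the rate of change in logIL-6 over baseline, 3 and 6 months, with a within-person correlation of 0.54. Both compare whole arms. Neither mentions the qualifying marker, and the t-test has no baseline term. The documents do not state what share of entrants is expected to qualify on TNFR1 alone.

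**The concern.** The entry rule can bring together two kinds of participant who differ, by construction, on the variable to be analysed: those with IL-6 at or above the threshold and those below it. Because IL-6 at screening predicts IL-6 six months later, the split is prognostic for the outcome. An unadjusted t-test leaves that predictable spread in the error term. Without stratification, the arms of a 60-person trial can also end up with visibly different mixes.

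There is a second, less certain possibility. If people with low starting IL-6 respond less on the log scale, the average effect across the whole arm is smaller than the effect in people with raised IL-6, and the planned 23 per group is too few. This pilot is meant to inform a larger trial. A null logIL-6 result from a mixed population, with nothing reported by entry marker, would be hard to interpret.

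**Working it through.** **Inputs from the protocol.** Two-sided alpha 0.05; 23 completers per group; effect 0.86 SD in logIL-6; 30 randomised per arm; correlation between repeated measurements 0.54 (all Section 7).

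**Assumptions (not in the documents).** *p* is the share entering on TNFR1 alone, taken as 20-50%. *r* is their logIL-6 effect relative to the others, taken as 0, 0.5 or 1.

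**1. The plan's own figure.** The noncentral t calculation for 0.86 SD gives n = 22.2, so 23 per group, with power 81.4%. The stated sample size reproduces; the point does not rest on an arithmetic error.

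**2. Chance imbalance.** With 60·*p* TNFR1-only entrants split at random into 30 and 30 (hypergeometric), a gap of 20 points means 6 or more people. The probability is 10% at *p* = 20% (12 people), 16% at 30% (18) and 20% at 50% (30).

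The size of the effect on the comparison follows if logIL-6 at entry and at 6 months is taken as bivariate normal with correlation 0.54 and the stratum is a cut of the entry value. The two strata then differ at entry by φ(z)/[p(1−p)] SD, where φ(z) is the normal density at the cut.
- *p* = 20%: 0.280/0.16 = 1.75 SD; at 6 months 0.54 × 1.75 = 0.94 SD; a 20-point gap moves the arm difference by 0.20 × 0.94 = 0.19 SD.
- *p* = 50%: 0.399/0.25 = 1.60 SD; at 6 months 0.86 SD; a 20-point gap moves it by 0.17 SD.

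This can go in either direction, so it is noise and not bias. It is about a fifth of the 0.86 SD effect.

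**3. Variance that adjustment would remove.** Under the same assumption the stratum explains R² = 0.54² × φ(z)²/[p(1−p)] of the 6-month variance, and the effective effect is 0.86/√(1−R²).

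| Analysis | R² | Effective effect | Power, 23 per group |
|---|---|---|---|
| Unadjusted t-test | 0 | 0.86 | 81% |
| Stratum, *p* = 20% | 0.292 × 0.490 = 0.143 | 0.93 | 87% |
| Stratum, *p* = 50% | 0.292 × 0.637 = 0.186 | 0.95 | 88-89% |
| Continuous baseline logIL-6 | 0.54² = 0.292 | 1.02 | 92% |

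Losing one or two degrees of freedom changes these figures by less than 0.1 point. If the correlation were only 0.4, the continuous covariate would give 0.86/√(1−0.16) = 0.94 SD and power of 87-88%.

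These rows read 0.86 SD as relative to the spread of the whole mixed population. If it is instead relative to the spread within a stratum, and the strata differ by 1 such SD, the unadjusted effect is 0.86/√(1+p(1−p)). That is 0.80 SD at *p* = 20% and 0.77 SD at 50%, with power of 75% and 72%, and a stratum term would restore about 81%. The two readings are alternatives and should not be added.

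**4. Conditional dilution.** Overall effect = 0.86 × [1 − p(1 − r)]; unadjusted t-test, 23 per group.

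| Response in TNFR1-only entrants | *p* = 20% | *p* = 30% |
|---|---|---|
| Same proportional fall (*r* = 1) | 0.86 SD, 81% | 0.86 SD, 81% |
| Half (*r* = 0.5) | 0.77 SD, 73% | 0.73 SD, 68% |
| None (*r* = 0) | 0.69 SD, 63% | 0.60 SD, 52% |

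This takes 0.86 SD as the effect in people with raised IL-6. The *r* = 1 row is before any added variance.

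**The case against.** The strongest objection is that dilution is not established. The outcome is on the log scale, so an equal proportional fall at every starting level leaves the mean effect unchanged, and the documents give neither the share of TNFR1-only entrants nor their response. That stands: dilution can be stated only as a possibility. It does not answer the variance and imbalance argument, which holds even when the response is equal.

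A second objection is that the rate-of-change analysis uses each person's own baseline, so starting imbalance matters less there. That also stands, but it leaves the 6-month t-test, which is the analysis that sets 23 per group, unadjusted.

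Three stronger readings are tempting and are not supported.

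- A reader might infer that the benchmark in Section 7 ("adequate power to detect a difference similar to the 0.63 SD (or 2.5 pg/mL) difference observed") cannot occur in someone starting below 2.5 pg/ml, or applies only to people with raised IL-6. The text reports a raw-scale difference observed at the end of a randomised study and does not call it a within-person fall. The documents do not give that study's entry IL-6.
- A reader might apply 0.63 SD to the t-test, where power at 23 per group is 55%. Section 7 ties that benchmark to the longitudinal analysis and plans the t-test for 0.86 SD.
- A reader might infer that the combined index in Section 3 should be an outcome because "an inflammatory index (IIS) combining serum levels of IL6 and sTNFR1 provided superior prediction of 10-year mortality". That result, and the gait-speed comparison in Table 1, concern prediction in a cohort, not response to treatment, and an index of two levels is not the same as an either-threshold rule. Nor is a gain in power assured. For an equal-weight index with an assumed between-marker correlation of 0.4, power at 23 per group is 93% if both markers move 0.86 SD (effect 0.86 × √(2/1.4) = 1.03). It is 40% if only IL-6 moves (0.86/√2.8 = 0.51), against 81% for IL-6 alone.

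**Conclusion.** The point holds in a limited form. The either-marker entry rule allows a population that is mixed on the analysed variable, and the 6-month comparison neither balances nor adjusts for that mix. The t-test remains valid; what is lost is precision. With the plan's 0.54 correlation, a bivariate-normal model and a 20-50% share, adjustment would lift power from 81% to 87-92%. Stratification would also remove a 10-20% chance of a 20-point imbalance. The share is an assumption, and the 0.54 comes from another cohort and may differ in people selected for raised markers.

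Dilution is a risk to be acknowledged, not a finding. Depending on an unstated response, power at a 20-30% share lies between 52% and 81%. Stratification and covariate adjustment do not undo dilution, but recording the stratum makes it visible.

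**What to change.** 1. Stratify the randomisation by entry marker: IL-6 at or above the threshold versus TNFR1 only. State which test decides the stratum, so that people whose qualifying marker changes between screening and retest are classified in advance.
2. In Section 7, replace the unadjusted 6-month t-test with an analysis of covariance of logIL-6 that includes that stratum and continuous baseline logIL-6.
3. State the expected share of TNFR1-only entrants, and say that 0.86 SD for the whole arm presumes a similar proportional response in them.
4. Report estimates by entry marker descriptively only: a 20% share leaves 0.20 × 23 = 4.6, about 5 completers per arm.

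The combined index is at most an optional exploratory measure.

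The cost is a two-level list for the pharmacy, one or two model degrees of freedom and a few sentences in Section 7. The retest result is already needed for eligibility and blood is already drawn at the baseline visit, so no new sample is required. No entry threshold or treatment rule changes.
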